CRITERIA FOR EVALUATION: Safety: The following safety outcome measurements will be assessed: 
• Incidence of AEs and SAEs• Vital signs (heart rate, blood pressure, respiratory rate, and temperature)• Physical examination (including neurological assessment)• Hip clinical assessment• Laboratory test results (urinalysis, chemistry, hematology)• Electrocardiogram (ECG)		

NAME OF COMPANY BioMarin Pharmaceutical Inc. [name]	SUMMARY TABLE Referring to Part of the Dossier: Volume: Page:	FOR NATIONAL AUTHORITY USE ONLY:
NAME OF FINISHED PRODUCT: BMN 111		
NAME OF ACTIVE INGREDIENT: Modified rhCNP	Reference:	

 • Echocardiogram • Anti-BMN 111 immunogenicity assessments • Cortisol levels • Prolactin levels 		

Efficacy: The following efficacy outcome measurements will be assessed:
 
 • Change from baseline in AGV • Change from baseline in length/height Z-score 
Pharmacokinetics: Whenever possible, the following PK parameters will be estimated by non-compartmental analysis:
 
 • Area under the plasma concentration-time curve from time 0 to infinity (AUC_{0-∞}) • Area under the plasma concentration-time curve from 0 to the time of last measurable concentration (AUC_{0-t}) • Maximum plasma concentration (C_{max}) • Time to reach C_{max} (T_{max}) • Elimination half-life (t_{1/2}) • Apparent clearance of drug (CL/F) • Apparent volume of distribution based upon the terminal phase (V_z/F) 
Drug accumulation after repeat-dose administration will also be evaluated. PK parameters at Week 13, 26, 39 and 52 will be compared to Day 1. The impact of immunogenicity (if present) on PK will also be evaluated.
 
Bone metabolism and BMN 111 pharmacodynamic biomarkers:
 
 • Changes in bone and collagen metabolism and BMN 111 activity will be assessed. 
Clinical outcome assessments:
 
 • Bayley-III • WeeFIM • CBCL • ITQOL 
Exploratory: The following exploratory measurements will be assessed:
 
 • Upper:lower body segment ratio • Imaging assessments (X-rays of the spine and lower extremities) • MRI to define skull and brain morphology (including dimensions of foramen magnum, ventricular and brain parenchymal dimensions) • Sleep study • Clinical photography (optional) 		

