Sentinel subjects from each cohort will be enrolled and studied for short-term safety and PK data, after which subjects in all 3 cohorts will be randomized to receive BMN 111 or placebo SC daily (1:1 ratio) for up to 52 weeks. No two sentinel subjects will be dosed on the same day for any cohort. At the start of the study, 3 sentinel subjects will be enrolled and monitored in Cohort 1. After all 3 sentinel subjects reach Day 8, the Sponsor will review and evaluate all available safety data and Day 1 PK data. Based on PK data and criteria set in the protocol, the dose may be adjusted for the sentinel subjects and the rest of the cohort, and will be the starting dose for the younger cohort sentinel subjects. Upon review of the clinical and PK data, the remainder of Cohort 1 (≥ 27 additional subjects) will be enrolled and randomized to treatment with BMN 111 or placebo (1:1 ratio). After the sentinel subjects complete 12 weeks of dosing, a DMC review will occur to evaluate all available safety and PK data. Upon approval by the DMC, the next younger cohort (Cohort 2) will be opened and the 3 sentinel subjects will be enrolled.

The same procedure will be followed for Cohort 2. After all 3 sentinel subjects reach Day 8, the Sponsor will review and evaluate all available safety data and Day 1 PK data. Based on PK data and criteria set in the protocol, the dose may be adjusted for the sentinel subjects and the rest of the cohort, and will be the starting dose for the younger cohort sentinel subjects. Upon review of the clinical and PK data, the remainder of Cohort 2 (≥ 17 additional subjects) will be enrolled and randomized to treatment with BMN 111 or placebo (1:1 ratio). After the sentinel subjects complete 12 weeks of dosing, a DMC review will occur to evaluate all available safety and PK data. Upon approval by the DMC, the youngest cohort (Cohort 3) will be opened and the 3 sentinel subjects will be enrolled.

The same procedure will be followed for Cohort 3. After all 3 sentinel subjects reach Day 8, the Sponsor will review and evaluate all available safety data and Day 1 PK data. Based on PK data and criteria set in the protocol, the dose may be adjusted for the sentinel subjects and the rest of the cohort, and will be the starting dose for the younger cohort sentinel subjects. Upon review of the clinical and PK data, the remainder of Cohort 3 (≥ 17 additional subjects) will be enrolled and randomized to treatment with BMN 111 or placebo (1:1 ratio).

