2. Heart rate, blood pressure, and respiratory rate should be taken and recorded at each indicated time point.

3. When blood samples and vital sign assessments are scheduled at the same time or within the same time window, vital signs should be measured before blood samples are drawn.

4. If a vital sign measurement must be taken after a blood draw, ensure adequate analgesia for the blood draw and wait several minutes before measuring vital signs.

5. Vital signs may be monitored more frequently or for longer duration post-dose as clinically indicated.

6. If a subject has a hypotensive event, or signs potentially consistent with hypotension, or a decrease of 20 mm Hg systolic BP or more from baseline (defined by pre-dose vitals collected that day), vital signs should be measured and recorded approximately every 15 minutes (\pm 5 minutes) for the first hour and every 30 minutes (\pm 5 minutes) thereafter until the BP returns to baseline (or within the normal range for this subject as defined by PI) and signs (if present) resolve.

7. If the decision is made to adjust the dose, vital signs will be obtained for at least 4 hr following the first dose at the adjusted dose level, similar to the Day 3, 8 schedule.

8. If a dose adjustment visit coincides with a visit at which a full PK is drawn, vital signs will be obtained for 8 hours, similar to the Day 1,2 schedule.

^h A standard 12-lead ECG will include heart rate, rhythm, intervals, axis, conduction defects, and anatomic abnormalities. The time of collection will be recorded. ECGs should be performed in triplicate with the subject supine at the visits indicated in the Schedule of Events. ECGs will be performed post-dose on study day visits at which a dose is given; in addition, on Day 1, ECGs will be performed pre-dose. On days when PK samples are being drawn, ECGs should be performed within a 5-minute window prior to 30-minute PK assessment.

ⁱ Echocardiogram is obtained at the early termination visit only if the previous assessment was done more than 3 months prior to early termination.

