9.1.1 Dose Adjustments

Analysis of available PK data from studies 111-101 and 111-202 indicated that differences in subject body weight did not directly translate to differences in total body clearance of BMN 111. The same weight-based dose in the pediatric population of Study 111-202 (5-12 years old) yielded lower exposure (C_{max} and AUC) than that characterized in the adult population of Study 111-101. Therefore, the same weight-based dose in the young pediatric population in this study may yield exposure less than the target exposure range characterized to be safe and effective in Study 111-202 at the 15- μ g/kg dose. Since this is the first experience with BMN 111 in this young pediatric population, it is also possible the exposure at 15 μ g/kg could be greater than the target exposure range, and dose adjustment may be warranted. Thus, an option for adjustment of the weight-based dose is provided to ensure that the appropriate target exposure for safety and efficacy is reached for the young subjects in this study.

The need for dose adjustment will be evaluated as follows: three sentinel subjects in Cohort 1 will receive an initial dose of 15 μ g/kg. After all three sentinel subjects reach Day 8, the Sponsor will review and evaluate all available safety and PK data (at minimum). If the criteria for dose adjustment are met, the three sentinel subjects will be started on the new adjusted dose at their next scheduled visit, and vital signs will be obtained for at least 4 hours post-dose.

The remainder of the subjects in the age cohort will also be enrolled starting at the new adjusted dose. After the third sentinel subject reaches Week 12 post dose adjustment, a DMC review will occur to evaluate all safety and PK data and, upon endorsement, the three sentinel subjects from the next younger cohort will be enrolled starting at the new adjusted dose. The three sentinel subjects for the second and third cohorts will be evaluated similarly to the sentinel subjects in the first cohort for potential dose adjustment.

As subjects age on study, they will be administered the dose determined to be appropriate for their current age. For example, if a subject enrolls into Cohort 2 at age 20 months, they will receive the recommended dose for subjects aged ≥ 6 to < 24 months until they turn 24 months in age. When they turn 24 months in age, they will begin to receive the recommended dose for subjects aged ≥ 24 to < 60 months.

Criteria for Dose Adjustment

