The criteria for dose adjustment are based on obtaining equivalent exposure characterized to be safe and effective with the 15- μ g/kg dose in Study 111-202 in each of the age cohorts evaluated in this study. BMN 111 dose may be adjusted if the mean observed AUC_{0-120} from

sentinel subjects is less than the 25th percentile for AUC₀₋₁₂₀ in Cohort 3 (15 µg/kg) of Study 111-202 or greater than the 75th percentile in Cohort 3 of Study 111-202. If these criteria are met, an allometric scaling coefficient, α , for BMN 111 clearance by subject body weight will be determined using a population PK modelling approach and available data from this study and Studies 111-202 and 111-101. The recommended adjusted dose will be determined using the following expression:

$$Dose_{ch} = Dose_{ref} \left(\frac{WT_{ch}}{WT_{ref}} \right)^\alpha$$

where WT_{ref} and $Dose_{ref}$ are the typical (i.e., median) subject body weight and total dose, respectively, at the 15 µg/kg dose level in Cohort 3 of Study 111-202, and WT_{ch} is the anticipated median weight in the age cohort being studied. As such, the recommended adjusted dose will target the median AUC₀₋₁₂₀ observed at the 15 µg/kg dose level of Study 111-202. The recommended adjusted dose, $Dose_{ch}$, will be normalized by WT_{ch} , to provide the recommended adjusted weight-based dose. The following rules will be used for dose adjustment:

- A maximum of a 2-fold increase in dose/kg will be permitted between dose adjustments regardless of exposure.
- The total dose will not exceed the highest total dose administered in Study 111-202.

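### After an upward dose adjustment, section 9.1.1 releases the rest of a cohort on the new dose using sentinel data from the old dose only

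*Protocol*

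**What the plan says.** At the starting dose the gate is explicit (section 9.1): "After all 3 sentinel subjects reach Day 8, the Sponsor will review and evaluate all available safety data and Day 1 PK data". Only after that review is the remainder of the cohort enrolled and randomized: at least 27 children in Cohort 1 and at least 17 in each of Cohorts 2 and 3.

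If mean sentinel AUC0-120 lies below the 25th or above the 75th percentile of the 15 µg/kg group in Study 111-202, section 9.1.1 allows a new dose to be calculated from a population PK model. The sequence is then:

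- Sentinels: "the three sentinel subjects will be started on the new adjusted dose at their next scheduled visit".
- Monitoring (Table 9.1.1, vital signs notes): "vital signs will be obtained for at least 4 hr following the first dose at the adjusted dose level". A further note reads "If a dose adjustment visit coincides with a visit at which a full PK is drawn, vital signs will be obtained for 8 hours".
- Remainder of the same cohort: "The remainder of the subjects in the age cohort will also be enrolled starting at the new adjusted dose".
- DMC: a review once the third sentinel reaches Week 12 after the adjustment, and then "upon endorsement, the three sentinel subjects from the next younger cohort will be enrolled starting at the new adjusted dose".

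Two limits apply. One is on each step: "A maximum of a 2-fold increase in dose/kg will be permitted between dose adjustments regardless of exposure". The other holds the total dose to the highest given in Study 111-202. The synopsis and section 15 let the DMC endorse dose adjustments where needed, but do not require it. After Day 1, the synopsis places sentinel PK as follows: "PK parameters at Week 13, 26, 39 and 52 will be compared to Day 1".

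**The concern.** The design rests on three children meeting a dose first and the others following once those three have been reviewed. When the dose is raised, that order is not carried over. Every observation behind the release comes from the old dose, and the new dose is a model prediction. Nothing requires the remainder to wait for a sentinel safety or exposure result at the new dose, or even for the sentinels' first injection of it.

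The Week 12 DMC review does not fill the gap, because it governs the next younger cohort. For Cohort 3, the youngest children, no cohort follows and so no later gate exists.

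If the scaling coefficient alpha is underestimated, the remainder starts above target exposure. The acute risk is hypotension, in children whom section 9.1 recognizes may be unable to describe symptoms.

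**Working it through.** **1. The two sequences compared.** The document states no figure to reproduce, so the first check is of procedure.

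- Starting dose: sentinels dosed, Day 1 PK, safety to Day 8, Sponsor review, remainder released.
- Raised dose: decision made on old-dose data, sentinels switch at their next visit, remainder enrolled on the new dose. No review stands between the last two steps.

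**2. Timing of sentinel PK.** After Day 8 the next visits are Week 3 and Week 6, and neither has scheduled PK. A switch at Week 3 leaves 13 − 3 = 10 weeks to the next sentinel profile. A switch at Week 6 leaves 13 − 6 = 7 weeks.

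**3. The dose per kg implied by the protocol's expression.** Dividing by cohort weight, with 15 µg/kg as the reference:

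dose per kg = 15 × (WT_ref / WT_ch)^(1 − alpha)

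The protocol gives no weights and no alpha. Assumed here: WT_ref 20 kg, WT_ch 5 kg, true alpha 0.75, sentinels starting at 15 µg/kg, and exposure proportional to dose.

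- Needed dose: 15 × 4^0.25 = 21.2 µg/kg.
- Exposure at 15 µg/kg: 15 / 21.2 = 0.71 of target.
- Dose if alpha is estimated as 0.50: 15 × 4^0.50 = 30 µg/kg, exactly the 2-fold cap.
- Overshoot: 30 / 21.2 = 1.41.

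**4. Comparison with the protocol's own limits.** For an assumed log-normal AUC, the quartiles relative to the median are exp(±0.6745σ), with σ² = ln(1 + CV²):

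- CV 30%: 25th percentile 0.82, 75th percentile 1.22.
- CV 40%: 0.77 and 1.30.
- CV 50%: 0.73 and 1.38.

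Starting exposure of 0.71 is below the 25th percentile in all three cases, so the trigger is met. The 1.41 overshoot is above the 75th percentile in all three.

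**5. Sensitivity to reference weight** (5 kg cohort, full 2-fold step, true alpha 0.75):

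- WT_ref 15 kg: need 19.7, overshoot 30 / 19.7 = 1.52.
- WT_ref 25 kg: need 22.4, overshoot 1.34.
- WT_ref 30 kg: need 23.5, overshoot 1.28.

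The last two pass the limit only at the lower CVs: 1.34 is below 1.38, and 1.28 is below 1.30.

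**6. How large the error in alpha must be.** With WT_ref / WT_ch = 4, overshoot = 4^(true alpha − estimated alpha). Passing 1.22 needs an underestimate of ln 1.22 / ln 4 = 0.14. Passing 1.38 needs ln 1.38 / ln 4 = 0.23. An estimate of 0.65 gives 15 × 4^0.35 = 24.4 µg/kg, an overshoot of 24.4 / 21.2 = 1.15, which is inside the limit.

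**7. Which cohorts.** For alpha of 0 or more, the multiple cannot exceed WT_ref / WT_ch. At WT_ref 20 kg, a 2-fold step needs a median weight of 10 kg or less even at alpha 0. At an assumed weight ratio of 0.6 and alpha 0.5, the multiple is 0.6^(−0.5) = 1.29. Large steps therefore belong to the lightest children.

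**The case against.** The strongest case against is that the raised dose is neither arbitrary nor untested. It is given only where measured exposure was low, it aims at a median already studied, and the model uses the sentinels' own data together with Studies 111-101 and 111-202. A capped first step from 15 reaches 30 µg/kg, which section 9.4.6 reports as well tolerated overall at ages 5 to 14 and section 7.4 as similar in safety to 15 µg/kg. Each randomized child has a Day 1 PK profile and 8 hours of observation on Days 1 and 2. Stopping criteria apply, extra sentinels may be added, and the total dose is capped. Screening bloods fall between Day −30 and Day −14, so if screening follows the Day 8 review, nobody in the remainder is dosed before about the Week 3 visit. The DMC Charter is not shown and may add a step.

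Most of this stands and limits the likely harm. It does not replace the missing review. The caps and the model bound or predict exposure, the stopping criteria act after an event, and the screening interval yields no sentinel data at the new dose.

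Three stronger readings are tempting but unsupported:

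- A reader might infer that 27 Cohort 1 children face a doubled dose. At a 20 kg reference weight, that needs a cohort median of 10 kg or less, and the protocol gives no weights to suggest it.
- A reader might take the more than proportional rise in exposure at 30 µg/kg and multiply 0.71 by 2^1.2 or 2^1.4, giving 1.62 or 1.87 times target. That derives the need under proportionality and then abandons proportionality, and the protocol states no exponent. If 21.2 µg/kg is the need, the consistent figures are (30 / 21.2)^1.2 = 1.52 and (30 / 21.2)^1.4 = 1.62, still on assumed exponents.
- A reader might infer that no PK exists at the new dose for 7 to 10 weeks. That is true of scheduled sentinel PK only.

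**Conclusion.** The gap is real and should be closed. Section 9.1.1 releases the remainder of a cohort on a raised dose without the sentinel review that it requires at the starting dose. It weighs most in Cohorts 2 and 3, with about 8 children on BMN 111 in each at the minimum size, and Cohort 3 lacks even a later DMC gate.

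The overshoot of about 1.4 illustrates what one plausible set of inputs allows. It depends on assumed weights, an alpha underestimated by 0.25, proportional exposure and a log-normal AUC. With alpha correctly estimated, the formula lands on target under proportionality, and the documents do not show how likely a large error is. They do not support a claim that the raised dose is unsafe. They support only that it is not checked in the sentinels before the rest of the cohort may receive it.

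**What to change.** In section 9.1.1 and the matching synopsis text:

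1. Before the remainder of a cohort is enrolled on an upward-adjusted dose, the three sentinels receive it first. The Sponsor repeats its existing safety review about 7 days later and releases the remainder if no stopping criterion is met. Where the per-visit blood limit allows, move one scheduled sentinel PK profile to the switch visit, shifting that visit's other blood tests if needed. Then also require mean AUC0-120 not above the existing 75th-percentile limit. A profile after Week 13 is the better one to move, so that the Week 13 profile still precedes the DMC review.
2. Require DMC endorsement before any cohort receives more than 30 µg/kg, the highest per-kg dose in Study 111-202. This is a gate, not a cap. It is needed because the 2-fold limit applies to each step.

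Costs arise only if the dose is raised. Release of the remainder is held to 14 + 7 = 21 days after Day 8 (Week 3 switch) or 35 + 7 = 42 days (Week 6 switch), plus assay time if PK is used. The sentinels lose one later profile if it is moved. Blood volume at the switch visit rises unless other tests are shifted, because Weeks 3 and 6 already carry clinical laboratory draws. Cohort 3 treatment must start between about 13 and 26 weeks of age, so a few infants may age into Cohort 2.

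Three children are a weak safety screen: the chance of at least one event, 1 − (1 − p)^3, is 14%, 27% and 49% at assumed rates of 5%, 10% and 20%. That is why the PK criterion is worth adding where blood volume permits.

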9.1.2 Stopping Criteria

Individual Subject Stopping Criteria

For individual subjects treated with BMN 111, DMC will be informed if any of the following individual subject stopping criteria should occur. Temporary dosing suspension, permanent discontinuation of dosing, or dose reduction for the individual subject will be considered.

- Any treatment-emergent adverse event (AE) assessed as at least Grade 4 by the Investigator and/or Sponsor Medical Monitor
- Any treatment-emergent AE of at least Grade 3 assessed as related to study drug by the Investigator and/or Sponsor Medical Monitor
- Any two treatment-emergent Grade 2 symptomatic hypotension events within 7 days (non-urgent medical intervention indicated) or any Grade 3 hypotensive event (urgent medical intervention or hospitalization indicated) assessed by the Investigator and/or Sponsor's Medical Monitor
- Clinically significant finding or arrhythmia on ECG that indicates abnormal cardiac function or conduction or prolongation of QTc-F >500 msec

- Clinically significant new or worsening signs of cervicomedullary compression as determined by the Investigator and in consultation with Sponsor medical monitor and neurosurgical specialist (if needed)
- Adverse findings on clinical hip exam or hip imaging assessments that are determined to be clinically significant as determined by the Investigator and in consultation with Sponsor Medical Monitor and orthopedic specialist (if needed)

If the subject meets any stopping criterion, after Investigator consultation with the BioMarin Medical Monitor and DMC, the subject may be re-challenged at the same dose. If the subject meets stopping criteria on re-challenge or if re-challenge at same dose is not clinically indicated, other options that may be considered include:

- Re-challenge at lower dose with consideration given to upward titration to tolerated dose
- Permanent treatment discontinuation (with an option of ongoing assessment in the study)

Cohort Stopping Criteria

For each cohort, a DMC review will be conducted if any of the following cohort stopping criteria occur in subjects treated with BMN 111. Temporary dosing suspension, permanent discontinuation of dosing, or dose reduction for the cohort(s) will be considered and the impact on all other age cohorts will be assessed.

- Any treatment-emergent AE assessed as at least Grade 4 by the Investigator and/or Sponsor Medical Monitor
- Any two subjects have a treatment-emergent AE of at least Grade 3 assessed as related to study drug by the Investigator and/or Sponsor Medical Monitor
- Any two subjects have two treatment-emergent Grade 2 symptomatic hypotension events within 7 days (non-urgent medical intervention indicated) or any two subjects cohort have a Grade 3 hypotensive event (urgent medical intervention or hospitalization indicated) assessed by the Investigator and/or Sponsor's Medical Monitor
- Any two subjects have a clinically significant finding or arrhythmia on ECG that indicates abnormal cardiac function or conduction or prolongation of QTc-F >500 msec
- Any two subjects have adverse findings on clinical hip exam or hip imaging assessments that are determined to be clinically significant as decided by principal investigator and in consultation with Sponsor medical monitor and orthopedic specialist (if needed)

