
NAME OF COMPANY BioMarin Pharmaceutical Inc. [name]	SUMMARY TABLE Referring to Part of the Dossier: Volume: Page:	FOR NATIONAL AUTHORITY USE ONLY:
NAME OF FINISHED PRODUCT: BMN 111		
NAME OF ACTIVE INGREDIENT: Modified rhCNP	Reference:	
As subjects age on study, they will be administered the dose determined to be appropriate for their current age. For example, if a subject enrolls into Cohort 2 at age 20 months, they will receive the recommended dose for subjects aged ≥ 6 to < 24 months until they turn 24 months in age. When they turn 24 months in age, they will begin to receive the recommended dose for subjects aged ≥ 24 to < 60 months. Duration of the study is 52 weeks of treatment with a safety follow up at Week 56. Following completion of the study, subjects in all treatment groups may be eligible to receive BMN 111 in an open-label extension study, to assess safety and efficacy of BMN 111 over the longer term; and to study the long-term outcomes on sustained growth, proportionality, bone maturation and medical comorbidities.		
For subjects enrolling into the extension study, safety follow up visit at Week 56 will be waived.		
Data Monitoring Committee (DMC) In addition to safety and PK monitoring by BioMarin personnel, an independent DMC will act as an advisory body to BioMarin and will monitor the safety and PK of subjects in the study. After the sentinel subjects complete 12 weeks of dosing, a DMC review will occur to evaluate all available safety and PK data. Upon approval by the DMC, the next younger cohort will be opened and the 3 sentinel subjects will be enrolled. The DMC will make recommendations for stopping or continuing the study on an individual subject level and/or on a cohort level per the pre-specified stopping criteria. Based on criteria outlined in the protocol, the DMC may also make endorsements for dose adjustments if needed. Please see DMC Charter for further details.		

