9.3.2 Exclusion Criteria

Individuals who meet any of the following exclusion criteria will not be eligible to participate in the study:

1. Have hypochondroplasia or short-stature condition other than achondroplasia (e.g., trisomy 21, pseudoachondroplasia, etc.)
2. Subject weighs < 5.0 kg (Cohort 1 and 2) or < 4.0 kg (Cohort 3)
3. Have any of the following:
 - Hypothyroidism or hyperthyroidism
 - Insulin-requiring diabetes mellitus
 - Autoimmune inflammatory disease (including celiac disease, systemic lupus erythematosus, juvenile dermatomyositis, scleroderma, etc.)
 - Inflammatory bowel disease
 - Autonomic neuropathy
4. Have a history of any of the following:
 - Renal insufficiency defined as serum creatinine > 2 mg/dL
 - Chronic anemia or Hgb < 10.0 g/dL (based on screening clinical laboratory testing)
 - Baseline systolic blood pressure (BP) below age and gender specified normal range or recurrent symptomatic hypotension (defined as episodes of low BP generally accompanied by symptoms e.g., dizziness, fainting) or recurrent symptomatic orthostatic hypotension
 - Cardiac or vascular disease, including the following
 - Cardiac dysfunction (abnormal echocardiogram determined to be clinically significant by PI and medical monitor) at Screening Visit
 - Hypertrophic cardiomyopathy
 - Pulmonary hypertension
 - Congenital heart disease with ongoing cardiac dysfunction
 - Cerebrovascular disease
 - Aortic insufficiency or other clinically significant valvular dysfunction
 - Clinically significant atrial or ventricular arrhythmias
5. Have a clinically significant finding or arrhythmia that indicates abnormal cardiac function or conduction or QTc-F > 450 msec on screening ECG
6. Have evidence of cervicomedullary compression (CMC) likely to require surgical intervention within 60 days of Screening as determined by the Investigator and informed by the following assessments:

- Physical exam (e.g., neurologic findings of clonus, opisthotonus, exaggerated reflexes, dilated facial veins)
- Polysomnography (e.g., severe central sleep apnea)
- MRI indicating presence of severe CMC or spinal cord damage

7. Have an unstable medical condition likely to require surgical intervention in the next 6 months, or planned spine or long-bone surgery (i.e., surgery involving significant disruption of bone cortex) during the study period

8. Have documented uncorrected Vitamin D deficiency: 25(OH)D \leq 15 ng/mL (37.5 nmol/L)

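### Cervicomedullary compression is the only individual stopping criterion with no cohort counterpart, so outside the scheduled 12-week review some clusters would require no cohort-level DMC review

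*Protocol*

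**What the plan says.** Section 9.1.2 has two lists with different consequences. For the individual list, "DMC will be informed if any of the following individual subject stopping criteria should occur", and suspension, discontinuation or dose reduction is considered for that child. The list has six entries: any Grade 4 or higher event, a related Grade 3 or higher event, hypotension, an ECG finding, CMC and hip findings. The CMC entry, "Clinically significant new or worsening signs of cervicomedullary compression as determined by the Investigator" (with the Medical Monitor and, if needed, a neurosurgeon consulted), carries no grade or causality condition.

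For the cohort list, "a DMC review will be conducted if any of the following cohort stopping criteria occur in subjects treated with BMN 111", dosing action is considered for the whole cohort, and "the impact on all other age cohorts will be assessed". This list has five entries, and none names CMC. The amended Synopsis carries the same two lists. It also says that DMC recommendations are made "on an individual subject level and/or on a cohort level per the pre-specified stopping criteria", and it points to the DMC Charter for details.

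**The concern.** Section 7.4 ranks CMC as the gravest complication of achondroplasia and links it to sudden death. Children with milder CMC can enter, because exclusion 6 in Section 9.3.2 removes only those who "Have evidence of cervicomedullary compression (CMC) likely to require surgical intervention within 60 days of Screening". Prior decompression surgery is possible in Cohort 1 with the Medical Monitor's agreement (exclusion 15, note). Table 9.1.1 schedules brain and skull MRI only at screening and Week 52, or at early termination, so clinical signs are the main warning during treatment.

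The protocol therefore treats worsening CMC as grounds to consider stopping one child's dosing, but a second or third case in the same cohort does not by itself oblige anyone to ask whether the cohort, or a younger cohort already open, should continue. Hypotension, ECG and hip findings each become a cohort question at the second subject, with no relatedness test.

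**Working it through.** No stated figure is in dispute, so the main check is a comparison of the two lists in amended Section 9.1.2.

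| Individual criterion | Cohort counterpart |
|---|---|
| Grade 4 or higher event, any cause | Yes, at one subject |
| Related Grade 3 or higher event | Yes, at two subjects |
| Hypotension | Yes, at two subjects |
| ECG finding or QTc-F above 500 msec | Yes, at two subjects |
| CMC | None |
| Hip findings | Yes, at two subjects |

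Five of six are carried forward and one, CMC, is not.

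CMC can reach a cohort criterion only through the two general adverse-event lines:

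- One Grade 4 or higher CMC case meets the first line. Table 10.2.3.2.1 places urgent intervention at Grade 4, so urgent CMC is covered at the first case.
- Two Grade 3 cases meet the second line only if each is "assessed as related to study drug by the Investigator and/or Sponsor Medical Monitor". A call by either assessor is enough.
- Two Grade 3 cases that neither assessor calls related meet none of the five lines.
- Two Grade 2 cases meet none of the five lines, whatever the causality call.

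The third route is the realistic one. Table 10.2.3.3.1 classes an event as unrelated when another cause is likely, and CMC is a known complication of the disease. The Grade 2 route is thin: Grade 2 implies minimal or noninvasive intervention, while Section 7.4 describes decompression surgery as the only treatment for CMC. The two Section 10 tables come from the earlier protocol version in the file, because amended Section 10 is not in the text supplied.

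**How often would a two-subject line fire on background disease alone?** The protocol gives no rate of clinically significant CMC signs, so the rates below are assumptions.

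Treated subjects per cohort at the planned minimum (Section 9.1):

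- Cohort 1: 3 sentinels + 13 or 14 of 27 randomized = 16 or 17.
- Cohorts 2 and 3: 3 sentinels + 8 or 9 of 17 randomized = 11 or 12.

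With n treated subjects, independent and each with probability p over 52 weeks:

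P(at least 2) = 1 − (1 − p)^n − n·p·(1 − p)^(n−1)

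Example, n = 12 and p = 0.05: 1 − 0.540 − 0.341 = 0.118 (from unrounded terms).

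| n | p = 0.02 | p = 0.05 | p = 0.10 | p = 0.20 |
|---|---|---|---|---|
| 11 | 0.020 | 0.102 | 0.303 | 0.678 |
| 12 | 0.023 | 0.118 | 0.341 | 0.725 |
| 16 | 0.040 | 0.189 | 0.485 | 0.859 |
| 17 | 0.045 | 0.208 | 0.518 | 0.882 |

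These are probabilities that the line fires. Extra reviews would be somewhat fewer, because some clusters would already have met the Grade 4 or related Grade 3 line. The range is too wide to predict the workload. It does show that the line should prompt a review and not an automatic hold.

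**The case against.** The case for leaving the lists alone is substantial.

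- **Visibility.** A reader might infer that the DMC would be unaware of a CMC cluster. The text does not support that. The DMC is told of every qualifying case in treated subjects and is consulted before re-challenge. Sections 9.1 and 9.1.1 also require it to review all available safety data after 12 weeks of sentinel dosing, before the next younger cohort opens. That is a required cross-cohort judgement, although it follows the calendar and need not capture later cases.
- **Sponsor review.** A hospitalized Grade 3 case would be a serious adverse event, reported within 24 hours whether or not called related. The sponsor evaluates such events against cumulative experience regardless of the investigator's causality call (Sections 10.1.2, 10.2.3.3 and 10.4.1, earlier version). This is a real safeguard, but it is not a DMC cohort review.
- **Deliberate choice.** A reader might also take the mismatch for an internal contradiction. It is not one: nothing says the lists must match, and the amendment revised CMC handling in exclusions 6 and 15 while leaving the cohort list as it was. Section 7.5.1 names hemodynamic and hip changes as nonclinical toxicities and does not list CMC, which Section 7.4 suggests treatment might improve. That could explain the omission, but the protocol gives no reason.
- **Interpretability.** Cohort lines count only treated children, so a count without a comparator says little about the drug when background disease is common, and a triggered review could hint at allocation. Both points stand. The existing lines also count treated children only, and a DMC review is where a comparison with placebo could be made.

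**Conclusion.** The point holds in a limited form. CMC is the one criterion of six without a cohort counterpart. Outside the 12-week sentinel review, the protocol as shown requires no cohort-level review or cross-cohort assessment for two or more treated children in a cohort with clinically significant CMC below Grade 4 that is not a related Grade 3 event. What is missing is an obligation to ask the cohort question; the DMC already has the information. The practical gap is mainly Grade 3 CMC attributed to the disease.

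This rests on three things: the earlier version's grading and causality tables, because amended Section 10 is not shown; the absence of a trigger in the DMC Charter, which cannot be checked; and an unknown CMC rate, so the probability of an uncovered cluster cannot be stated. It is a cheap improvement of optional to modest priority.

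**What to change.** Add one line to the cohort criteria in Section 9.1.2 and the same line to the Synopsis: *any two subjects meet the individual-subject CMC criterion, regardless of attributed causality*. Referring back to the individual criterion keeps its judgement process: the Investigator decides, in consultation with the Medical Monitor and, if needed, a neurosurgical specialist. The model is the existing hip line, "Any two subjects have adverse findings on clinical hip exam or hip imaging assessments that are determined to be clinically significant". As with the other cohort lines, meeting it should trigger DMC review, with any dosing action only considered. If the Charter already has such a trigger, a cross-reference from Section 9.1.2 would be enough.

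The cost is two lines of text and some additional reviews by a committee that already exists. Some of those reviews would be prompted by background disease, at a frequency the protocol does not allow to be estimated.
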